An additional sensitivity analysis will done for an alternative definition of persistent disability, considered as 'new onset' persistent disability, defined as an increase from baseline of >=4 points in WHODAS scores that persists for at least 6 months. The definition of time to the first of new-onset persistent disability or death will use the same principles as for the primary endpoint.

Secondary endpoints

- 1. Death/survival: all-cause mortality at 90 days, and survival up to 12 months after surgery.
- 2. A composite (pooled) and individual incidence of 30-day mortality and major septic complications, where the latter is defined as the composite of sepsis, surgical site infection, anastomotic leak and pneumonia at 30 days post-surgery. [Detailed clinical definitions are provided in the Protocol]
- 3. Acute Kidney Injury (AKI): according to the Kidney Disease: Improving Global Outcomes group criteria, but not urine output—for Stage 2 or worse AKI defined as at least twofold increase in creatinine, or estimated glomerular filtration rate decrease >50%.

Since a restrictive intravenous fluid regimen may artificially elevate serum creatinine due to a smaller dilutional effect from less intravenous fluids, we will calculate adjusted creatinine following the approach of Liu (2011, Reference 1 below), where

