adjusted creatinine = serum creatinine × (1 + cumulative fluid balance/total body water), and assuming that total body water is 60% of body weight, expressed in mL. Serum creatinine is measured on days 1 and 3 and the maximum value in the patient's hospital stay. We will apply adjustments to creatinine levels at days 1 and 3 only. Fluid intake will be accumulated using IV fluids administered intraoperatively, in recovery, and on days 1 to 3 postoperatively, plus the volume of any blood transfusions administered. Fluid outputs from the time of surgery to Day 1 post-surgery will be accumulated using the recorded urine outputs, blood losses and volumes in surgical drains. Missing fluid output components will be imputed to prevent adjustment factors being missing when creatinine levels are present. Fluid outputs on days 2 and 3 are not recorded, so these will be estimated under the assumption of a net fluid balance of zero on each of days 2 and 3; this will form the principal analysis. Sensitivity to this assumption will be assessed using two alternatives: (a) assuming a zero cumulative fluid balance at day 3, and (b) assuming the ratio of intake to outputs up to day 1 persists on days 2 and 3. These two assumptions enclose that of the principal analysis.

We will also report the use of renal replacement therapy up to 90 days after surgery; and delta-creatinine, defined as the difference between the maximum (fluid-adjusted) postoperative serum creatinine level and the preoperative serum creatinine level.

- 4. Pulmonary oedema: documented evidence of respiratory distress or impaired oxygenation and radiological evidence of pulmonary oedema.
- 5. Duration of mechanical ventilation: Defined as additive over all episodes up to 90 days after surgery. This will be reported as (a) the proportion of patients requiring ventilation; and (b) the duration of ventilation in patients receiving ventilation.
- 6. Inflammation: plasma C reactive protein concentration on day 3 after surgery.
- 7. Tissue perfusion marker: peak serum lactate concentration within 24 hours of surgery.
- 8. Any blood transfusion: including red cell, fresh frozen plasma or platelet transfusion, from the initiation of surgery; and quantity of transfusion in patients receiving each product.
- 9. Unplanned admission to HDU/ICU within 30 days of surgery.
- 10. Total HDU/ICU stay in patients admitted to HDU/ICU, including initial admission and readmission duration up to day 30

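### The fluid correction stops at day 1 and day 3 creatinine, while the in-hospital maximum is left raw and the eGFR basis is unstated, so part of the dilution bias may remain in AKI and delta-creatinine

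*SAP*

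**What the plan says.** SAP, Secondary endpoints, item 3, gives the reason for the correction: "Since a restrictive intravenous fluid regimen may artificially elevate serum creatinine due to a smaller dilutional effect from less intravenous fluids". The formula is "adjusted creatinine = serum creatinine × (1 + cumulative fluid balance/total body water"), with body water taken as 60% of weight.

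Four statements in that item bear on this point:

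- Values collected: "Serum creatinine is measured on days 1 and 3 and the maximum value in the patient's hospital stay".
- Values corrected: "We will apply adjustments to creatinine levels at days 1 and 3 only".
- Delta-creatinine: "the difference between the maximum (fluid-adjusted) postoperative serum creatinine level and the preoperative serum creatinine level".
- AKI: "at least twofold increase in creatinine, or estimated glomerular filtration rate decrease >50" per cent. The rule does not name the postoperative values, the eGFR equation, or whether eGFR is computed from corrected creatinine.

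Outputs on days 2 and 3 are not recorded. The principal analysis therefore rests on the "assumption of a net fluid balance of zero on each of days 2 and 3", with two alternatives as sensitivity analyses. No sensitivity analysis addresses how the maximum or the eGFR branch is handled.

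Protocol Section 3.3.3.2, item 7, has the same two-branch AKI rule, but its formula multiplies fluid balance by 0.5. The SAP formula has no such multiplier.

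**The concern.** The SAP accepts that raw creatinine is not comparable between arms, then leaves one of its three collected values raw. If the peak falls on day 2 or after day 3 and the recorded maximum counts, a raw value decides the case. For delta-creatinine the fluid-adjusted label then conflicts with the restriction to days 1 and 3. If delta-creatinine instead means the larger of the two corrected values, the recorded maximum has no stated use. The eGFR branch raises the same question, because the correction is written for creatinine only.

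Two analysts could follow this text and obtain different AKI counts. Using raw values pushes the comparison in a known direction, towards more AKI under restriction. AKI is analysed as a risk ratio and is also one of the endpoints for the SAP's subgroup analyses.

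**Working it through.** The plan states no AKI rate, event count or power for this endpoint, so there is no planned figure to reproduce.

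**1. Correction factors.** For a 75 kg patient, body water is 0.6 × 75 = 45 L, and F = 1 + balance/45.

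- Pilot 24 h intake (protocol Section 2.6) was 3167 mL restrictive and 5133 mL liberal. Assuming 2000 mL output in both arms, balances are 1.167 and 3.133 L, so F = 1.026 and 1.070. The liberal factor is 4.3% larger.
- The Trial Summary targets of about 2.5 and 5.5 L, with the same output, give F = 1.011 and 1.078, a gap of 6.6%.
- With the protocol's 0.5 multiplier the gaps are 2.2% and 3.3%.

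**2. Risk ratio with no true effect.** Let r be the true peak-to-baseline ratio, log-normal. A case decided on raw creatinine needs r/F ≥ 2, that is r ≥ 2F. F is larger in the liberal arm, so fewer liberal patients qualify.

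Example at pilot volumes, with true AKI 5% and SD of log r 0.35 (both assumed):

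- Mean of log r = 0.693 − 1.645 × 0.35 = 0.117.
- Restrictive: P(r ≥ 2 × 1.026) = 4.29%. Liberal: P(r ≥ 2 × 1.070) = 3.31%. Ratio 1.30.
- If only a share q is decided raw, each arm's rate is (1 − q) × 5% + q × raw rate. At q = 0.25 the rates are 4.82% and 4.58%, ratio 1.05.

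Results with the SAP formula:

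| Share decided on raw values | Central set | Pilot volumes | Wide set |
|---|---|---|---|
| 25% | 1.03–1.05 | 1.04–1.05 | 1.03–1.11 |
| 50% | 1.06–1.11 | 1.08–1.12 | 1.07–1.26 |
| All | 1.13–1.30 | 1.18–1.30 | 1.15–1.75 |

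- Central set: assumed balances paired as 1 vs 2.5 L and 2 vs 4 L (restrictive vs liberal), SD 0.35–0.5, true AKI 5–8%.
- Pilot volumes: balances from step 1, with the central SD and AKI rates.
- Wide set: pilot and target volumes with 2000 mL output, true AKI 2–10%, median ratio m = 1.0–1.1, SD = (ln 2 − ln m)/z(1 − p), where p is the true AKI rate.

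With the 0.5 multiplier, the last row becomes 1.06–1.14, 1.08–1.14 and 1.07–1.32. If every contributing value is corrected, the ratio is 1.00 by construction.

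**3. Which peaks are exposed.** When balance is positive, a peak on day 1 or day 3 is covered, because its corrected value exceeds the raw one. The artefact remains only for peaks on other days, or through eGFR if that is raw.

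**4. Delta-creatinine.** At a true creatinine of 100 µmol/L, a raw peak shifts the between-arm difference by 100/1.026 − 100/1.070 = 4.0 µmol/L (pilot), or 100/1.011 − 100/1.078 = 6.1 µmol/L (targets).

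**5. eGFR branch.** The documents name no equation. If eGFR varies as creatinine to the power −a, it halves at a rise of 2^(1/a). Corrected doubling needs a raw rise of 2/F. It therefore adds a case beyond raw eGFR only if F > 2/2^(1/a).

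| a (assumed) | Raw rise that halves eGFR | F needed | Balance needed at 75 kg |
|---|---|---|---|
| 1.0 | 2.00 | above 1 | above 0 L |
| 1.154 | 1.823 | 1.097 | 4.36 L |
| 1.209 | 1.774 | 1.127 | 5.73 L |

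If eGFR is raw and the exponent is at the steep end, the correction would seldom decide AKI status at the balances in step 1. At a = 1.0 this problem disappears.

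**6. Day-2 peaks.** Under zero net balance on days 2 and 3, the day-1 cumulative balance still holds on day 2. A peak known to fall on day 2 can take the day-1 factor without further fluid data.

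**The case against.** A reader might infer that AKI and delta-creatinine are computed from the uncorrected maximum and from raw eGFR, so that the full dilution bias stays in the endpoint. The documents do not support that. The AKI rule names no postoperative values, the eGFR basis is not stated, and delta-creatinine is expressly labelled fluid-adjusted, which can mean the larger of the corrected day 1 and day 3 values. Even on the adverse reading the bias is reduced, not left whole (step 3), and the risk ratios with every case decided raw are ceilings.

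Not correcting late peaks is also defensible. The SAP accumulates intake only to day 3 and has no recorded outputs after day 1. Its alternative of zero cumulative balance at day 3 implies a factor of 1, which matches leaving a later peak raw. Carrying a day-3 factor forward could over-correct the liberal arm. The calculation in step 2 applies day-1 factors even to late peaks, when excess fluid may have cleared. AKI is one of 13 secondary items, and renal replacement therapy to 90 days, which does not depend on a creatinine calculation, is reported beside it.

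These points limit the size and rule out a single corrected answer for late peaks. They do not remove the gap: the item lists the maximum, excludes it from the correction, and then refers to a fluid-adjusted maximum, with no sensitivity analysis for that choice.

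**Conclusion.** The concern holds in a conditional form. SAP item 3 does not settle which creatinine values enter AKI and delta-creatinine, and its restriction to days 1 and 3 leaves the recorded maximum raw. If that maximum or a raw eGFR can decide a case, part of the artefact that the SAP sets out to remove remains, in the direction of more apparent AKI under restriction.

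The likely size is modest: a null risk ratio of about 1.03–1.26 over the wide set if 25–50% of cases are decided raw, or 1.03–1.11 on the central set, where the ceiling is 1.13–1.30. The upper end of the wide set combines low AKI rates with full target separation in volume. The protocol's multiplier roughly halves each excess. All figures rest on assumed outputs, AKI rates and spread, and on the share of peaks off days 1 and 3, which the documents do not give.

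This should be fixed, as a matter of specification in a secondary safety endpoint. It does not touch the primary analysis.

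**What to change.** 1. State one set of values for both AKI and delta-creatinine. For the principal analysis, use corrected day 1 and day 3 creatinine plus the in-hospital maximum, with the maximum corrected when it is dated on or before day 3. A day-2 peak takes the day-1 balance under the SAP's own assumption.
2. For a maximum after day 3, or without a date, report both outcomes with it raw and with the day-3 factor carried forward. Treat the two results as bounds, since neither is clearly right.
3. Keep the eGFR branch, which is part of the protocol definition, but compute it from the corrected creatinine with one named equation.
4. Reconcile the SAP formula with the 0.5 multiplier in protocol Section 3.3.3.2, item 7, and state which applies.

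The cost is a few sentences of SAP text, a little code, one extra sensitivity analysis and one more assumption for late peaks. The documents do not say whether the date of the maximum is recorded. If it is not, every maximum that differs from the day 1 and day 3 values falls under step 2.

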 - (3) An abscess or other evidence of infection
 - (4) Diagnosis by surgeon or other physician
- iii) **Organ/space** Occurred within 30 days with no implant or within 1 year if an implant is in place this includes one or more of the following
 - (1) Purulent discharge
 - (2) Organisms identified
 - (3) Abscess or evidence of infection involving the organ/space on examination
 - (4) Diagnosis by surgeon or other physician
- 5. **Pneumonia:** The presence of new and/or progressive pulmonary infiltrates on chest radiograph plus two or more of the following:
 - (1) Fever ≥ 38.5°C or postoperative hypothermia <36°C
 - (2) Leukocytosis ≥ 12,000 WBC/mm³ or leukopenia < 4,000 WBC/mm³
 - (3) Purulent sputum and/or
 - (4) New onset or worsening cough or dyspnoea.
- 6. **Anastomotic leak:** A defect of the intestinal wall at the anastomotic site (including suture and staple lines of neorectal reservoirs) leading to a communication between the intra- an extra luminal compartments.
 - (1) Grade A anastomotic leakage results in no change in patients' management
 - (2) Grade B leakage requires active therapeutic intervention but is manageable without re- laparotomy
 - (3) Grade C anastomotic leakage requires re-laparotomy
- 7. Acute kidney injury: according to The Kidney Disease: Improving Global Outcomes (KDIGO) group criteria, but not urine output for Stage 2 or worse AKI defined as at least 2-fold increase in creatinine, or estimated GFR decrease >50%.(73) We also plan to report renal replacement therapy up to 90 days after surgery. Because a restrictive IV fluid regimen may artificially elevate serum creatinine due to a smaller dilutional effect from less IV fluids, we therefore calculated adjusted creatinine by first estimating the volume of distribution for creatinine as equal to total body water (assumed to be 60% of body weight, expressed in mL), and assuming that 50% of IV fluid was still accumulated as tissue oedema at the time of postoperative creatinine measurements.(74, 75) That is:

adjusted $Cr = SCr \times (1 + [0.5 \times fluid\ balance/total\ body\ water])$

- 8. Pulmonary oedema: respiratory distress or impaired oxygenation AND radiological evidence of pulmonary oedema
- 9. Duration of mechanical ventilation: additive, for all episodes up to 90 days after surgery
- 10. Inflammation: plasma C-reactive protein (CRP, using site-specific assay) concentration on Day 3
- 11. Tissue perfusion: peak serum lactate within 24 hours of surgery

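### No planned AKI or delta-creatinine analysis uses measured creatinine alone, so the effect of the fluid correction on the renal comparison cannot be seen

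*SAP*

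**What the plan says.** SAP, Secondary endpoints, item 3, takes AKI as KDIGO stage 2 or worse without the urine criterion: creatinine at least doubled, or estimated GFR more than halved. It then gives a reason for correcting creatinine: "a restrictive intravenous fluid regimen may artificially elevate serum creatinine due to a smaller dilutional effect from less intravenous fluids". The formula is "adjusted creatinine = serum creatinine × (1 + cumulative fluid balance/total body water"), "assuming that total body water is 60% of body weight, expressed in mL".

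The remaining rules in the same item are:
- Day 1, day 3 and the in-hospital maximum are the creatinine values available. Only days 1 and 3 are corrected.
- Outputs to day 1 are recorded, and missing components are imputed. Outputs on days 2 and 3 are not recorded.
- The principal analysis takes net balance as zero on each of days 2 and 3.
- "Sensitivity to this assumption will be assessed using two alternatives: (a) assuming a zero cumulative fluid balance at day 3". Alternative (b) lets the intake-to-output ratio up to day 1 continue over days 2 and 3. The SAP adds: "These two assumptions enclose that of the principal analysis".
- Delta-creatinine is defined on the fluid-adjusted maximum. Renal replacement therapy to 90 days is reported.

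Protocol section 3.3.3.2, item 7, also plans a corrected creatinine, but applies 0.5 to the fluid balance, "assuming that 50% of IV fluid was still accumulated as tissue oedema at the time of postoperative creatinine measurements".

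**The concern.** The correction is a function of the randomised exposure. When balances are positive the factor exceeds 1, and it is expected to be larger in the liberal arm because that arm receives more fluid. It therefore lowers the measured rise needed to reach a doubling, and lowers it more in the liberal arm.

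The sensitivity analyses vary only the unrecorded days. They leave the day-1 factor alone, although day 1 is when the assigned regimens have just diverged. Nothing elsewhere fills the gap. The SAP's additional sensitivity analyses change covariates or impute missing outcomes, and the AKI subgroup analyses keep the same endpoint.

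Renal safety is a main question about fluid restriction. If the corrected analysis shows no difference, or a benefit, a reader will want to know what the measured values show. The plan commits to no result that answers this.

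**Working it through.** **1. Volumes that feed the correction (75 kg, 4-h operation; protocol section 4.1).** The plan's own figures reproduce:
- Liberal: 10×75 + 8×75×4 = 3150 ml, plus 1.5×75×20 = 2250 ml, total 5400 ml.
- Restrictive: 5×75 + 5×75×4 = 1875 ml, plus 0.8×75×20 = 1200 ml, total 3075 ml.

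The pilot (protocol section 2.6) achieved 5133 and 3167 ml at 24 h, a gap of 1966 ml. The steps below use the pilot gap, which is smaller than the protocol's nominal gap of 5400 − 3075 = 2325 ml.

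**2. Which factors the planned analyses change.** Body water is 0.6×75 kg = 45,000 ml. As an illustration, assume 1500 ml output to day 1 in both arms and, for (b), 2000 ml intake over days 2–3.

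| Factor | Liberal | Restrictive |
|---|---|---|
| Day 1, all three analyses | 1 + (5133−1500)/45,000 = 1.081 | 1 + (3167−1500)/45,000 = 1.037 |
| Day 3, (a) | 1.000 | 1.000 |
| Day 3, principal | 1.081 | 1.037 |
| Day 3, (b) | 1.112 | 1.060 |

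Alternative (a) removes the correction on day 3 only. On these figures a corrected doubling on day 1 needs a measured ratio of 2/1.081 = 1.85 in the liberal arm and 2/1.037 = 1.93 in the restrictive arm, in every planned analysis.

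**3. Size of the shift.** The documents give no AKI rate, fluid output or creatinine spread, so these inputs are assumptions.
- Factor gap = 1966×(1−e)/45,000, where e is the fraction of the extra fluid excreted by day 1. At e = 0 it is 0.044; at e = 0.5 it is 0.022.
- Restrictive factors are assumed to be 1.03 and 1.01, so the liberal factors are 1.074 and 1.032.
- The peak creatinine ratio is log-normal with median 1 and P(ratio ≥ 2) = 5% measured in both arms, so σ = ln 2/1.645 = 0.421.
- Corrected AKI = 1 − Φ(ln(2/factor)/σ).

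| | Restrictive | Liberal | RR |
|---|---|---|---|
| e = 0.5 | 5.25% | 5.82% | 0.90 |
| e = 0 | 5.77% | 7.00% | 0.82 |

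Per 1500 patients, added liberal cases are 1500×(0.0582−0.05) ≈ 12 to 1500×(0.0700−0.05) = 30. Added restrictive cases are 1500×(0.0525−0.05) ≈ 4 to 1500×(0.0577−0.05) ≈ 12. At an assumed measured AKI of 2% the RR is 0.86 to 0.75; at 8% it is 0.92 to 0.86.

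**4. Protocol coefficient.** Using 0.5 halves the factor gap to about 0.011–0.022, and the RR at 5% becomes about 0.95 to 0.90.

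**5. The reverse assumption.** Suppose instead that the corrected values are the truth and true AKI is 5% in both arms. A measured doubling then needs a true ratio of at least 2×factor. Measured AKI is 4.76% v 4.28% (RR 1.11) at e = 0.5, and 4.32% v 3.48% (RR 1.24) at e = 0.

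**The case against.** The strongest reply is that the correction is there to remove a bias. If dilution is real, equal measured AKI means more true AKI in the liberal arm, and the shift in step 3 is the intended repair. Step 5 shows that the measured analysis would then be the misleading one. This stands. A reader might infer that the correction hides renal harm from restriction, but the documents do not show that. They show only that the planned results cannot separate repair from over-correction.

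Four further points also stand in part.
- **Classification rule.** The SAP never says in words that corrected creatinine replaces measured creatinine when AKI is classified. It attaches the fluid-adjusted label to delta-creatinine, not to the AKI definition. That every AKI analysis rests on corrected values is an inference from the principal-analysis wording. On either reading, no measured-only analysis is named.
- **In-hospital maximum.** It is uncorrected. If it counts towards AKI, a positive-balance correction cannot remove a measured doubling; it can only add cases, and later peaks get no factor. If half of the at-risk peaks fell on corrected days (an assumption), the RR at 5% would be about 0.95 to 0.90.
- **Enclosing.** A reader might take the SAP's statement about enclosing as wrong. It is true for what it covers, the balance on days 2 and 3, and the SAP does not claim to enclose zero correction.
- **Oliguria.** Low urine output raises the factor, but it does so in either arm, so it gives no clear direction of error.

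Renal replacement therapy does not depend on the correction and is a real check, but a partial one, because it is not the AKI endpoint.

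**Conclusion.** The point holds as a missing analysis. The principal analysis and both alternatives share one day-1 factor, delta-creatinine is also adjusted, and neither document names an analysis on measured creatinine. With positive balances the correction moves the AKI contrast towards restriction, and the plan cannot show by how much.

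Under the stated assumptions the correction alone gives an RR of about 0.90 to 0.82. This is an upper range for those inputs, because it treats every peak as corrected. The size also depends on the volumes: the nominal volume gap would widen it, and the protocol coefficient would narrow it to about 0.95 to 0.90. The direction needs only a larger positive balance in the liberal arm.

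Since equal true AKI would give a measured RR of about 1.11 to 1.24, neither version is self-evidently unbiased. A reader might go further and require both analyses to agree before concluding that there is no renal harm. The SAP plans no such conclusion, so that rule does not follow from the documents. This is a cheap improvement to a secondary safety endpoint.

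**What to change.** Three changes to SAP item 3:
1. Prespecify AKI and delta-creatinine on measured creatinine at all time points, with the same models as the corrected analyses. Report them beside the corrected results as the zero-correction end of the sensitivity range.
2. State which values (day 1, day 3, in-hospital maximum) classify AKI, and how the uncorrected maximum enters delta-creatinine.
3. Reconcile the SAP coefficient of 1 with the protocol coefficient of 0.5, and give the reason for the one kept.

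The cost is a few sentences and one more model run per outcome on data already held. The downside is that two AKI results may differ and both must then be interpreted. Fixing the pair in advance avoids a choice between them after the data are seen.
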